Listing 16.2.4.4 – Prior and Concomitant Medications/Treatments	42
Listing 16.2.4.5 – Non-Pharmacological Interventions (NPIs)	43
Listing 16.2.4.6 – Vital Signs and Urine Pregnancy Test at Baseline	44
Listing 16.2.4.7 – Vision Evaluation.....	45
Listing 16.2.4.8 – Lip Function, Lip Sensation and Lip Movement/Function Tests	46
Listing 16.2.4.9 – Lip Texture, Lip Firmness and Lip Symmetry Evaluations	47
Listing 16.2.5.1 – Treatment Administration at Visit 1/Day 1	48
Listing 16.2.6.1 – Efficacy Evaluations of Lip Fullness Grading Scale and Perioral Lines at Rest Severity Scale	49
Listing 16.2.6.2 – Efficacy Evaluations of Subject Satisfaction with Lips, Swelling and Global Aesthetic Improvement.....	50
Listing 16.2.7.1.1 – Adverse Events (Related to Vascular Injections/Visual Events).....	51
Listing 16.2.7.1.2 – Adverse Events (Excluding Vascular Injections/Visual Events).....	52
Listing 16.2.7.2.1 – Adverse Events (Related to Vascular Injections/Visual Events) Leading to Study Treatment Interrupted/Discontinued	52
Listing 16.2.7.2.2 – Adverse Events (Excluding Vascular Injections/Visual Events) Leading to Study Treatment Interrupted/Discontinued	52
Listing 16.2.7.3.1 – Serious Adverse Events (Related to Vascular Injections/Visual Events).....	52
Listing 16.2.7.3.2 – Serious Adverse Events (Excluding Vascular Injections/Visual Events).....	52
Listing 16.2.7.4 – Adverse Events (Related to Vascular Injections/Visual Events) Lasted more than 30 Days	52

Statistical Analysis Plan

1 Purpose of Statistical Analysis Plan

The purpose of the statistical analysis plan is to describe in detail all the data, statistical methods, and summary tables required to implement the statistical analysis of Clinical Study Protocol PRO 2018-03 (Section 8 in the study protocol version 2.0, dated November 13, 2018).

2 Study Objectives

To evaluate the safety and efficacy of retreatment with PN40082 for lip augmentation.

3 Study Design and Sample Size Determination

3.1 Study Design

For the purpose of exploring the above objectives, the study will be conducted as a multicenter, open-label clinical study of retreatment with PN40082 of subjects seeking lip augmentation who initially received treatment with either PN40082 or Restylane Silk in the prior PRO 2018-02 study. Subjects meeting the inclusion/exclusion criteria will receive a single additional treatment with PN40082.

Visits will occur at:

- Visit 1 / Day 1 – baseline and treatment. This is the same visit as Visit 5 (Day 168) of Protocol PRO 2018-02.
- Visit 2 / Day 28 (± 2 days) / Month 1 – interim visit
- Visit 3 / Day 56 (± 4 days) / Month 2 – End of Study (EOS) Visit.

Telephone contacts for safety follow-up will occur at:

- Day 3 (± 2 days) - Safety follow-up telephone call
- Day 14 (± 2 days) – Safety follow-up telephone call
- Day 168 (± 7 days) / Month 6 – Safety follow-up telephone call

Evaluations include:

- Lip Fullness Grading Scale (LFGS) (Overall lip fullness considering both lips together, fullness of the upper lip and fullness of the lower lip)
- Perioral lines at rest severity scale (POL) (Overall perioral lines at rest severity considering both lips together, perioral lines at rest severity of the upper lip and perioral lines at rest severity of the lower lip)
- Patient Global Aesthetic Improvement (pGAI)
- Investigator Global Aesthetic Improvement (iGAI)
- Swelling Assessment
- Subject Satisfaction with Lips Assessment (using VAS)

Safety will be assessed by monitoring adverse events (AEs) and concomitant medications at all study visits. Other Safety evaluations include lip function, lip sensation, lip texture, lip firmness, lip symmetry and lip movement/function. Other evaluations include Investigator Ease of Use Assessment.

3.2 Sample Size Determination

The maximum sample size was determined by the number of subjects who completed the prior PRO 2018-02 study and elected retreatment with PN40082

4 Populations To Be Analyzed

All retreated subjects will be included in the analysis.

5 Planned Analyses

5.1 Methodological Considerations

All the data points for the retreatment period will be presented in subject data listings. No inferential statistical analyses will be performed. SAS software (version 9.4 or higher) will be used for all data analyses and tabulations.

Efficacy and safety data will be summarized overall and also broken down by the treatment arm in PRO 2018-02.

5.2 Handling of Dropouts or Missing Data

All summaries will be generated using the available data without imputation for the missing values.

5.3 Demographics and Baseline Characteristics

Demographic and baseline characteristic variables (including age, sex, race, ethnicity, and Fitzpatrick skin type) will be tabulated using descriptive statistics. For each continuous variable, the summary will include the mean, standard deviation (SD), median, minimum and maximum. For each categorical variable, the summary will include frequencies and percentages.

5.4 Subject Accountability

A summary of subject disposition will be provided for all subjects descriptively, including reason for discontinuation.

5.5 Efficacy Variables

Key efficacy assessments include the following:

- LFGS: 0 = very thin, 1 = thin, 2 = moderately thick, 3 = thick, 4 = full
- POL: 0 = None (a mouth with no perioral lines), 1 = Mild (a mouth with a few shallow perioral lines), 2 = Moderate (a mouth with some moderate lines), 3 = Severe (a mouth with many deep lines or crevices)
- Subject Satisfaction with Lips using a visual analog scale (VAS) on a 100-mm scale from 0 = Very Unsatisfied to 100 = Very Satisfied
- Patient Global Aesthetic Improvement (pGAI) Score: 1=Worse, 2=No change, 3=Improved, 4=Much improved, 5=Very much improved
- Investigator Global Aesthetic Improvement (iGAI) Score: 1=Worse, 2=No change, 3=Improved, 4=Much improved, 5=Very much improved
- Swelling Assessment: 0 = None, 1 = Minimal, 2 = Mild, 3 = Moderate, 4 = Severe

5.5.1 Efficacy Analysis

For LFGS and POL, actual values will be summarized by visit. Change from baseline in this study and change from baseline in the prior controlled study (PRO 2018-02) will also be summarized at Visit 2/Month 1 and Visit 3/Month 2. Summary statistics include mean, SD, minimum, median, and maximum.

Other efficacy variables including pGAI, iGAI, and Swelling Assessment will also be tabulated by visit using frequencies and percentages.

5.6 Safety Variables

Key safety variables include incidence rate of treatment-emergent adverse events (TEAEs) and the exposure to the study product, as well as Investigator Ease of Use Assessment, lip function, lip sensation, lip texture, lip firmness, lip symmetry, and lip movement/function.

5.6.1 Adverse Events

All adverse events (AEs) occurring during the study will be recorded and coded in the Medical Dictionary for Regulatory Activities (MedDRA), version 20 or higher. TEAEs are defined as events that appear subsequent to the open-label injection or that were present prior to the open-label injection but worsened in intensity after the open-label injection.

TEAEs (those related to vascular injections/Visual events, separate from those that were not related to vascular injections/Visual events) for the retreated subjects will be summarized grouped by the number of injections that were received of PN40082, or Restylane Silk during the prior controlled study (PRO 2018-02). Frequency and percent of subjects reporting TEAEs of injection site will be tabulated by preferred terms, and further by severity and relationship to study device. In summaries of severity and relationship, subjects who reported more than one event in a treatment arm that are mapped to the same preferred term will be counted only once in that treatment arm under the strongest severity and relationship, respectively.

TEAEs related to vascular injections/Visual events will also be tabulated by subject Fitzpatrick Skin Type (I-III vs. IV-VI), each Fitzpatrick Skin Type individually and by number of injections subjects received.

Treatment-Emergent Serious Adverse Events (TESAEs) and TEAEs that led to treatment interruption or discontinuation will be presented in data listings.

5.6.2 Exposure to PN40082

Amount of syringe used for open-label retreatment will be summarized using descriptive statistics (mean, SD, minimum, median, maximum) at Visit 1 for all retreated subjects.

5.6.3 Other Variables

Investigator Ease of Use Assessment

Overall ease of use of the device will be evaluated by the Treating Investigator using the numerical rating scale (NRS) from 0 being not easy to 10 being most easy at Visit 1/Day. It will be summarized for all retreated subjects descriptively with mean, SD, minimum, median, and maximum.

Lip Evaluations

Lip function, lip sensation, lip texture, lip firmness, lip symmetry, and lip movement/function will be evaluated by the Blinded Evaluating Investigator at each visit. These variables will be summarized using frequency and percent of subjects by categories of incidence.

Concomitant Medications

Concomitant medications will be coded using the World Health Organization (WHO) Drug Dictionary, Version March 2013 or later, and will be presented in data listings.

6 Tables and Listings

The following is an example of tables and listings that will be included in the clinical study report. Tables and listings may be modified as needed during the data analyses.

7 Appendices

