Table 14.3.3.3 – Treatment-Emergent Adverse Events (TEAEs) Excluding Vascular Injections/Visual Events by MedDRA System Organ Class, Preferred Term, and Causality

Table 14.3.3.4 – Treatment-Emergent Adverse Events (TEAEs) Excluding Vascular Injections/Visual Events by MedDRA System Organ Class, Preferred Term, and Number of Injections

With footnote regarding data source change to “Source: Listing 16.2.7.1.2”.

Table 14.3.4.1 – Lip Function and Lip Sensation Tests by Visit

Study Visit	Category	PRO 2018-02 PN40082	PRO 2018-02 Restylane Silk	Total
Was the subject able to sip liquid through a straw?				
Visit 1/Day 1 (Prior to injection)	N	0	0	0
	n (%) Yes	0 (0%)	0 (0%)	0 (0%)
Visit 2/Month 1	N	0	0	0
	n (%) Yes	0 (0%)	0 (0%)	0 (0%)
Visit 3/Month 2	N	0	0	0
	n (%) Yes	0 (0%)	0 (0%)	0 (0%)
Was the subject able to feel sensation of a 0.4G monofilament at three points on the upper lip and three points on the lower lip?				
Visit 1/Day 1 (Prior to injection)				
...				
Was the subject able to feel sensation of a cotton wisp at three points on the upper lip and three points on the lower lip?				
Visit 1/Day 1 (Prior to injection)				
...				

Source: Listing 16.2.4.8

O:\Studies\Prollenium\SYM 2018-03\Biometrics\Programs\Tables\xxx.sas ran on Month Day, Year at hh:mm on data from Month, Day, Year.

Table 14.3.4.2 – Lip Texture Evaluation by Visit

Study Visit	Category	PRO 2018-02 PN40082	PRO 2018-02 Restylane Silk	Total
Visit 1/Day 1 (Prior to injection)	N	0	0	0
	n (%) Normal	0 (0%)	0 (0%)	0 (0%)
	n (%) Abnormal	0 (0%)	0 (0%)	0 (0%)
	- n (%) Abnormal: Mild	0 (0%)	0 (0%)	0 (0%)
	- n (%) Abnormal: Moderate	0 (0%)	0 (0%)	0 (0%)
	- n (%) Abnormal: Severe	0 (0%)	0 (0%)	0 (0%)
Visit 2/Month 1	...			
	...			
Visit 3/Month 2				

Source: Listing 16.2.4.9

O:\Studies\Prolenium\SYM 2018-03\Biometrics\Programs\Tables\xxx.sas ran on Month Day, Year at hh:mm on data from Month, Day, Year.

Note:

Table 14.3.4.2 will be used as the shell for the following table:

Table 14.3.4.3 – Lip Firmness Evaluation by Visit

Table 14.3.4.4 – Lip Symmetry Evaluation by Visit

Table 14.3.4.5 – Lip Movement/Function Evaluation by Visit

Study Visit	Category	PRO 2018-02 PN40082	PRO 2018-02 Restylane Silk	Total
Visit 1/Day 1 (Prior to injection)	N	0	0	0
	n (%) Normal – Subject’s ability to pucker lips	0 (0%)	0 (0%)	0 (0%)
	n (%) Normal – Subject’s ability to blow with lips	0 (0%)	0 (0%)	0 (0%)
	n (%) Normal – Subject’s ability to pronounce words that begin with “W”	0 (0%)	0 (0%)	0 (0%)

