O:\Studies\ Prollenium\SYM 2018-03\Biometrics\Programs\Listing\xxx.sas ran on Month Day Year at hh mm on data from Month Day, Year.

Listing 16.2.4.7 – Vision Evaluation

Site- Subject	Treatment in PRO 2018-02	Study Visit (Time Point)	Subject wearing corrective lenses?	Confrontational Visual Field Results (Specify if abnormal), Assessed by	Ocular Visual Field Results (Specify if abnormal), Assessed by	Snellen Visual Acuity Score (SVAS)		SVAS Assessed by	Vision at Post-Baseline Visit	
						Left Eye	Right Eye		Changed significantly from PRO 2018-02 baseline?	If yes, the study ophthalmologist contacted?

O:\Studies\ Prolenium\SYM 2018-03\Biometrics\Programs\Listing\xxx.sas ran on Month Day Year at hh mm on data from Month Day, Year.

Listing 16.2.4.8 – Lip Function, Lip Sensation and Lip Movement/Function Tests

Site- Subject	Treatment in PRO 2018-02	Study Visit (Time Point)	Able to sip liquid through a straw?	Assessor of Lip Function	Able to feel sensation of a cotton wisp?	Able to feel sensation of a 0.4G monofilament	Assessor of Lip Sensation	Ability to pucker lips	Ability to blow with lips	Ability to pronounce words that begin with “W”	Assessor of Lip Movement /Function
------------------	-----------------------------	-----------------------------	--	--------------------------------	---	--	---------------------------------	------------------------------	---------------------------------	---	---

O:\Studies\ Prolenium\SYM 2018-03\Biometrics\Programs\Listing\xxx.sas ran on Month Day Year at hh mm on data from Month Day, Year.

Listing 16.2.4.9 – Lip Texture, Lip Firmness and Lip Symmetry Evaluations

Site- Subject	Treatment in PRO 2018-02	Study Visit (Time Point)	Lip Texture		Lip Firmness		Lip Symmetry	
			Normal or Abnormal (severity)	Evaluator	Normal or Abnormal (severity)	Evaluator	Normal or Abnormal (severity)	Evaluator

O:\Studies\ Prollenium\SYM 2018-03\Biometrics\Programs\Listing\xxx.sas ran on Month Day Year at hh mm on data from Month Day, Year.

Listing 16.2.5.1 – Treatment Administration at Visit 1/Day 1

Site-Subject	Treatment in	Injection placed successfully?	Site of Injection	Time of Injection	Amount of Syringe Used (ml)	Injection Techniques Used	Depth of Injection	Initials Who Performed Injection	Investigator Ease of Use Assessment	Evaluator

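### Lip safety evaluations are tabulated only as separate by-visit percentages, so the tables cannot show how many subjects became abnormal or worsened after retreatment

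*SAP*

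**What the plan says.** Protocol 7.9.2 names the six lip evaluations as other safety evaluations, and SAP 5.6 lists them among the key safety variables. Protocol 7.6.15 to 7.6.20 schedule each one before treatment at Visit 1 and again at Months 1 and 2. Protocol 7.7.6 also allows them at unscheduled visits.

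For the analysis, SAP 5.6.3 states that they will be "summarized using frequency and percent of subjects by categories of incidence". The shells carry this out as follows:

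- "Table 14.3.4.1 – Lip Function and Lip Sensation Tests by Visit" gives the number and percentage answering yes at each visit.
- "Table 14.3.4.2 – Lip Texture Evaluation by Visit" gives normal, abnormal and the three abnormal grades at each visit. It is also the shell for firmness and symmetry.
- "Table 14.3.4.5 – Lip Movement/Function Evaluation by Visit" gives the number and percentage normal on each task at each visit.

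In each shell the pre-injection assessment is a row of its own (its label begins "Visit 1/Day 1 (Prior to injection"), and the later visits are further rows. The columns are the two prior arms and the total. No shell crosses a subject's Visit 1 result with a later one, and none has a row for unscheduled visits.

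Subject-level data are covered separately. SAP 5.1 says: "All the data points for the retreatment period will be presented in subject data listings". The relevant listings are "Listing 16.2.4.9 – Lip Texture, Lip Firmness and Lip Symmetry Evaluations" and Listing 16.2.4.8, which holds the function, sensation and movement tests.

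**The concern.** The safety question for these measures is how many subjects became abnormal, or became worse, after retreatment. SAP 5.6.3 uses the word incidence, but the shells report prevalence at each visit. If some subjects start abnormal and return to normal while others move the opposite way, the percentages can stay level.

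The design makes movement in both directions plausible for some of the measures. The lips were filled about six months earlier, in some cases with a touch-up (Protocol 5). The grading thresholds are low: a side-to-side difference of 1 mm or less already counts as mild asymmetry (Protocol 7.6.19), and a lump that can be felt but not seen counts as mildly abnormal firmness (Protocol 7.6.18). The injector is also asked to aim for right-left symmetry (Protocol 7.4.2), so retreatment may itself correct an earlier asymmetry.

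Elsewhere the plan does look within subjects. LFGS and POL are summarized as change from two baselines (SAP 5.5.1), and treatment-emergent events are defined as new or worsened (SAP 5.6.1). The lip safety measures have no such summary.

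**Working it through.** **Inputs.** The plan gives no lip abnormality rate, power or error rate, so there is no figure to reproduce. The synopsis expects fewer than the 158 subjects enrolled in PRO 2018-02. The values of N and of the Visit 1 rates below are assumptions.

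**What by-visit tables determine.** Take N subjects seen at both visits, with b abnormal at Visit 1 and f abnormal at follow-up. Then:

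- net change = f − b, which the tables show;
- number newly abnormal lies between max(0, f − b) and min(f, N − b), and the tables do not narrow it further.

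**Example 1 (assumed).** N = 150 and b = 15, of whom 10 resolve; 10 others become abnormal.

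- Visit 1: 15/150 = 10%.
- Follow-up: f = 15 − 10 + 10 = 15, so 15/150 = 10%.
- Normal at Visit 1: 150 − 15 = 135. Newly abnormal: 10/135 = 7.4%.

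**Example 2 (assumed).** N = 120 and b = f = 24, so the table shows 20.0% at both visits. With 120 − 24 = 96 normal at Visit 1, that table fits each of these equally well:

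- 0 new and 0 resolved: 0/96 = 0.0%;
- 12 new and 12 resolved: 12/96 = 12.5%;
- 24 new and 24 resolved: 24/96 = 25.0%.

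**Range.** When the percentages are equal at both visits (b = f), the largest number of new cases that could be hidden is min(b, N − b). With b rounded to whole subjects:

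| Abnormal at both visits | N = 80 | N = 120 | N = 158 (ceiling) |
|---|---|---|---|
| 0% | 0 | 0 | 0 |
| 5% | 4 | 6 | 8 |
| 10% | 8 | 12 | 16 |
| 20% | 16 | 24 | 32 |
| 30% | 24 | 36 | 47 |

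If nobody is abnormal at Visit 1 and data are complete, the number new equals f and nothing is hidden.

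**Across the two follow-up visits.** Keep N = 120 and b = 24. Suppose 8 subjects are newly abnormal at Month 1 and recover by Month 2, when 8 different subjects are newly abnormal. Then 16/96 = 16.7% were newly abnormal at some point, against 8/96 = 8.3% at either visit. This is why a worst post-injection summary is needed as well as visit-specific shifts.

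**Denominators.** SAP 5.2 uses available data without imputation, so rows for different visits need not describe the same subjects. A percentage can move because of who attended, without any lip changing.

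**The case against.** The strongest reply is that the information is not lost. A reader might infer that change after retreatment goes unreported altogether. The documents do not support that: Listings 16.2.4.8 and 16.2.4.9 give each subject's results by visit, with severity for texture, firmness and symmetry. With fewer than 158 subjects, a determined reader could pair them. This stands, and it limits the point to what is tabulated. It does not remove it, because the count would have to be made by hand over six evaluations and several visits.

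A second reply is that treatment-emergent events are the stated safety endpoint and already capture new or worsened findings. This stands in part. The adverse event definition is broad enough to include an abnormal lip sign, but the text available for review (which lacks the opening of Protocol 7.9.7) contains no rule that an abnormal lip evaluation must be recorded as an event.

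Third, the by-visit tables do show net change, so a clear excess of new over resolved abnormalities would be visible. This is correct. The weakness is confined to offsetting movement.

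Fourth, a reader might infer that the tables would conceal real harm, and equally for all six measures. Neither follows. With a threshold as low as 1 mm, some new and resolved findings could be rating variation. If nearly all subjects pass the straw, sensation and movement tests at Visit 1 (an assumption), their tables lose almost nothing.

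Finally, the study is descriptive and SAP section 6 allows the shells to be modified. That makes the change easy, but does not commit anyone to it.

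**Conclusion.** The point holds as a gap in the planned summaries: SAP 5.6.3 and Tables 14.3.4.1 to 14.3.4.5 summarize the lip evaluations only visit by visit, and those percentages cannot separate new from resolved abnormalities. It is most plausible for texture, firmness and symmetry, and probably minor for function, sensation and movement.

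Its size is unknown, because it depends on the Visit 1 abnormality rate. The calculations show what the tables could fail to reveal under assumed rates and complete paired data; they do not predict that offsetting will occur. No sample size, error rate or decision rule is affected. The change is still worth making, because it supplies directly the number that the safety objective calls for.

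**What to change.** Keep Tables 14.3.4.1 to 14.3.4.5 and add to SAP 5.6.3 and the shells, by prior arm and total:

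- **Texture, firmness and symmetry:** shift tables from the pre-injection Visit 1 grade to the Month 1 grade, the Month 2 grade and the worst post-injection grade, with unscheduled visits included in the worst grade. Add a row for findings new or worsened since Visit 1, as n/N and percent, where N is subjects with both assessments.
- **Function, sensation and movement:** for each test, the number of subjects normal at Visit 1 who are abnormal at any later visit, over those normal at Visit 1 who have at least one later assessment.

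No new data are needed. The cost is a small amount of extra programming and a few more tables.

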7.1 Handling of Missing or Incomplete Dates for Adverse Events and Concomitant Medications

Adverse Events

Handling of partial dates is only considered for the start date. An adverse event with a partial start date is considered treatment emergent if:

- only the day is missing and the start month/year is the same or after the month/year of the first injection
- the day and month are missing and the start year is the same or greater than the year of the first injection date
- the start date is completely missing

Concomitant Medications

Handling of partial dates is only considered for the stop date. A medication with a partial stop date is considered concomitant if:

- only the day is missing and the stop month/year is the same or after the month/year of the first injection
- the day and month are missing and the stop year is the same or greater than the year of the first injection date
- the stop date is completely missing or the medication is ongoing.

